Appendix 2.2.3. Eczema Area and Severity Index (EASI)

The EASI quantifies the severity of a participant's AD based on both severity of lesion clinical signs and the percent of BSA affected. EASI is a composite scoring by the atopic dermatitis clinical evaluator of the degree of erythema, induration/papulation, excoriation, and lichenification (each scored separately) for each of four body regions, with adjustment for the percent of BSA involved for each body region and for the proportion of the body region to the whole body.

There are 4 lesion clinical signs for each of the 4 body regions (Appendix 2.2.2): erythema (E), induration/papulation (I), excoriation (Ex) and lichenification (L). For each of the lesion clinical signs, severity is scored on a 4-point scale: 0=absent, 1=mild, 2=moderate, and 3=severe. These 16 scores (0-3) are denoted as follows. Morphologic descriptors for each clinical sign severity score can be found in the study protocol.

Table 12. Symbols Denoting Lesion Clinical Signs by Body Region

Body Regions (row)/Clinical Signs (column)	Erythema (E)	Induration/Papulation (I)	Excoriation (Ex)	Lichenification (L)
Head and Neck (h)	Eh	Ih	Exh	Lh
Upper Limbs (u)	Eu	Iu	Exu	Lu
Trunk (including axillae and groin/genitals) (t)	Et	It	Ext	Lt
Lower Limbs (including buttocks) (l)	El	Il	Exl	Ll

In EASI scoring, each body region carries different body region weighting, the sum of these weightings is equal to 1: Head and Neck (0.1), Upper Limbs (0.2), Trunk (including axillae and groin/genitals) (0.3) and Lower Limbs (including buttocks) (0.4).

In each body region, the sum of the Clinical Signs Severity Scores for erythema, induration/papulation, excoriation, and lichenification is multiplied by the Area Score (Appendix 2.2.2) and by the body region weighting to provide a body region value (ie, body region subscore), which is then summed across all four body regions resulting in an EASI score as described in the following equation.

$$EASI = 0.1 Ah (Eh + Ih + Exh + Lh) + 0.2 Au (Eu + Iu + Exu + Lu) + 0.3 At (Et + It + Ext + Lt) + 0.4 Al (El + Il + Exl + Ll)$$

The EASI score can vary in increments of 0.1 and range from 0.0 to 72.0, with higher scores representing greater severity of AD. According to protocol's inclusion criteria, only participants with EASI \geq 16 at screening and baseline (Day 1) are included in this study. The following efficacy endpoints will be derived based on the EASI scores assessed at baseline and at post-baseline visits:

- Percent change from baseline in EASI score, defined as the change from baseline in EASI score divided by baseline EASI score, scaled to %.
- EASI-50, defined as a response if \geq 50% reduction from baseline in EASI score (as a pre-specified discontinuation criterion rather than an efficacy endpoint).
- EASI-75, defined as a response if \geq 75% reduction from baseline in EASI score.
- EASI-90, defined as a response if \geq 90% reduction from baseline in EASI score.

If any component score (BSA Area Score or lesion clinical sign severity score) in the equation is missing at a visit, the EASI will be missing at that visit. The derived endpoints will also be missing at that visit.

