Percent BSA with Atopic Dermatitis: The number of handprints of skin afflicted with atopic dermatitis in a body region can be used to determine the extent (%) to which a body region is involved with atopic dermatitis (Table 4). When measuring, the handprint unit refers to the size of each individual participant's hand with fingers in a closed position.

Table 4. Handprint Determination of BSA

Body Region	Total Number of Handprints in Body Region*	Surface Area of Body Region Equivalent of One Handprint*
Head and Neck	10	10%
Upper Limbs	20	5%
Trunk (including axillae and groin/genitals)	30	3.33%
Lower Limbs (including buttocks)	40	2.5%

^{*}Handprint refers to the hand size of each individual participant.

The extent (%) to which each of the four body regions is involved with atopic dermatitis is categorized to a numerical Area Score using a non-linear scaling method according to the following BSA scoring criteria (Table 5).

Percent BSA with Atopic Dermatitis in a Body Region	Area Score
0%	0
>0 - <10%	1
10 - <30%	2
30 - <50%	3
50 - <70%	4
70 - <90%	5
90 - 100%	6

Table 5. Eczema Area and Severity Index Score Criteria

Body Region Weighting: Each body region is weighted according to its approximate percentage of the whole body (Table 6).

Table 6. EASI Body Region Weighting

Body Region	Body Region Weighting
Head and Neck	0.1
Upper Limbs	0.2
Trunk (including axillae and groin/genitals)	0.3
Lower Limbs (including buttocks)	0.4

In each body region, the sum of the Clinical Signs Severity Scores for erythema, induration/papulation, excoriation, and lichenification is multiplied by the Area Score and by the Body Region Weighting to provide a body region value, which is then summed across all four body regions resulting in an EASI score as described in Equation 3.

Equation 3:
$$EASI = 0.1Ah(Eh+Ih+Exh+Lh) + 0.2Au(Eu+Iu+Exu+Lu) + 0.3At(Et+It+Ext+Lt) + 0.4Al(El+Il+Exl+Ll)$$

A = Area Score; E = erythema; I = induration/papulation; Ex = excoriation; L = lichenification; h = head and neck; u = upper limbs; t = trunk; l = lower limbs

The EASI score can vary in increments of 0.1 and range from 0.0 to 72.0, with higher scores representing greater severity of atopic dermatitis.

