6.2. Secondary and Exploratory Endpoints

6.2.1. Secondary Binary Endpoints

The EASI-75 response at Week 16 is the binary secondary efficacy endpoint in Part 1 DB phase. The analysis of the binary secondary endpoint will be based on Estimand E1 accounting for the intercurrent events using the FAS (Section 2.2.2, Appendix 3). This corresponds to the Estimand E1 including only the pre-intercurrent-event data (Appendix 3). For the secondary analysis, the normal approximation for the difference in binomial proportions adjusting for the actual stratification factor of baseline IGA (3 vs 4) via the CMH approach (Section 5.2.1.1) will be used. The baseline IGA is from the clinical database will be used as the actual stratification factor (Section 3.4.1). This CMH approach will be used to estimate the treatment difference in response rates of etrasimod 2 mg QD versus placebo and to generate 95% CI for the EASI-75 response rate difference at Week 16 along with the 2-sided p-value (Section 5.2.1.1). Missing values will be handled by setting the EASI-75

^[2] Only reasons with at least one participant in any group will be summarized.

response value to non-response, MR=NR (Section 5.3). This is the secondary analysis for EASI-75 response at Week 16.

Analysis of EASI-75 response at other visits prior to Week 16 (ie, exploratory endpoints) will also be analyzed using the same CMH method based on the Estimand E1 including pre-intercurrent-event data on the FAS.

Supportive analyses for EASI-75 for visits up to Week 16 will also be performed under the Estimand E1a using FAS (including all data). The same CMH approach adjusting to actual stratification factor (Section 3.4.1) will also be used. These analyses are to support the secondary analysis of estimating the treatment difference in response rates of etrasimod 2 mg QD versus placebo for EASI-75 at Week 16.

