These Area Scores (Ah, Au, At, and Al) of the four body regions will be used to derive the EASI score (Appendix 2.2.3). If any one of the four body regions has missing number of BSA handprints, the extent (%) of BSA in this body region will be missing and so will the Area Score for this body region. The total BSA (%) will also be missing.

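### The EASI scoring rule sets the score to missing for a blank that cannot change it, so a fully determined EASI-75 or EASI-90 responder in Part 1 can be counted as a non-responder

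*SAP*

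**What the plan says.** The EASI equation in SAP Appendix 2.2.3 works region by region. The sum of four sign scores "is multiplied by the Area Score (Appendix 2.2.2) and by the body region weighting to provide a body region value", and the four region values are added. Protocol Table 5 gives Area Score 0 to a region with 0% involvement.

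The missing-data rule follows in the same appendix: whenever "any component score (BSA Area Score or lesion clinical sign severity score) in the equation is missing at a visit, the EASI will be missing", and the appendix adds that "The derived endpoints will also be missing at that visit". Appendix 2.2.2 adds a feeder rule for the area component: "If any one of the four body regions has missing number of BSA handprints, the extent (%) of BSA in this body region will be missing"; the Area Score goes missing with it. Neither appendix exempts a region whose contribution is already fixed.

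What happens next depends on the endpoint and the part of the study.

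- **EASI-75 at Week 16 (SAP 6.2.1):** "Missing values will be handled by setting the EASI-75" response to non-response. SAP 5.3 applies the same rule to every missing binary efficacy endpoint in the Part 1 double-blind phase, including EASI-90, and in the extension.
- **Percent change in EASI under Estimand E2 (SAP 5.2.2.1):** an etrasimod participant with monotone missing values is imputed with placebo-group means at the missing visits, given that participant's earlier observed values. Intermittent gaps, and all gaps in the placebo group, are imputed as missing at random.
- **Part 2 (SAP 5.3 and 6.2.4):** missing responses are not imputed, and only observed values are summarised.

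**The concern.** A missing-data rule should act on values that are unknown. Here the rule also acts on values that the recorded data determine completely. A rater who records no involvement in a region and leaves one of its sign boxes empty has given everything the equation needs, yet the score is discarded. In Part 1 the discarded score then becomes a treatment failure.

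EASI-75 and percent change in EASI are the two secondary efficacy endpoints. EASI-75 is also one of the two efficacy measures named for the decision on starting Part 2 and completing the extension (Protocol 4.1, SAP 2.3). No planned analysis would reveal or undo the loss. The supportive Estimand E1a also turns missing into non-response, the E2a model leaves the value missing, and EASI-90 has no supportive analysis (SAP 5.3, 5.2.2.2 and 6.2.2).

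**Working it through.** **Inputs.** Region weights of 0.1, 0.2, 0.3 and 0.4, Area Scores 0 to 6, and four signs per region scored 0 to 3 (Protocol 8.2.2.2, SAP Appendix 2.2.3). The SAP introduces the signs with "These 16 scores (0-3) are denoted as follows". Minimum baseline EASI is 16 (Protocol 5.1). Planned size is 30 per arm (Protocol 9.5).

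**Reproducing the plan's figures.** With every Area Score 6 and every sign 3, EASI = (0.1 + 0.2 + 0.3 + 0.4) × 6 × 12 = 72.0, the stated maximum. The stated half-width for the IGA difference also reproduces: 1.96 × √(0.09 × 0.91/30 + 0.39 × 0.61/30) = 20.2%.

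**When a blank cannot matter.** A region's value is weight × Area Score × (sum of four signs).

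- If the Area Score is 0, the value is 0 whatever the signs are.
- If all four signs are 0, the value is 0 whatever the Area Score is.

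**Case 1, fully cleared.** All four Area Scores are 0 and the head-and-neck signs are blank. The equation gives EASI = 0.0, a 100% reduction. The written rule gives missing, hence non-response on EASI-75 and EASI-90.

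**Case 2, nearly cleared.** Head and neck has Area Score 0 with one sign blank. The other three regions each have Area Score 1 and a single mild sign. Then EASI = 0.1 × 0 × (blank) + 0.2 × 1 × 1 + 0.3 × 1 × 1 + 0.4 × 1 × 1 = 0.9, whether the blank is 0, 1, 2 or 3. From the lowest permitted baseline, the reduction is 1 − 0.9/16 = 94.4%, a response on both endpoints. The written rule again gives missing and non-response.

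**Size per participant.** 1/30 = 3.3 percentage points of the arm's response rate; two participants cost 6.7 and three cost 10.0. The following illustration uses assumed counts that are not in the documents, with unstratified normal-approximation intervals:

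| Etrasimod | Placebo | Difference | 95% CI |
|---|---|---|---|
| 12/30 | 3/30 | 30.0% | 9.4 to 50.6 |
| 11/30 (one lost) | 3/30 | 26.7% | 6.4 to 47.0 |
| 10/30 (two lost) | 3/30 | 23.3% | 3.3 to 43.3 |

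**Percent change under E2.** Week 16 is the last double-blind visit, so a score missing only there is monotone missing. An etrasimod participant in Case 1 would have a known −100% replaced by draws that use the placebo mean. Suppose the placebo mean is −25% to −50%. Putting that mean in directly would worsen the arm mean by (100 − 50)/30 = 1.7 to (100 − 25)/30 = 2.5 points. The SAP's imputation conditions on earlier visits, so this is too large for someone already doing well. As an illustration, assume an etrasimod mean of −60% at Week 12, a participant at −95%, and a regression coefficient of 0.75. The imputed centre moves by 0.75 × (−35) = −26.25 points beyond the placebo mean, to between −51.25% and −76.25%. The arm-mean loss is then (100 − 76.25)/30 = 0.8 to (100 − 51.25)/30 = 1.6 points. All of these inputs are assumed.

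**The case against.** The strongest reply is that the trigger may never occur. Each sign has a code for absent, the protocol has all four signs scored in all four regions by trained and qualified raters, and data are cleaned before the interim analysis. The documents do not show whether the CRF lets a blank be saved. The rule is also explicit, prespecified and worded identically for both arms. One participant's 3.3 points is small beside the 20.2-point half-width planned for IGA, in a study with no hypothesis test. A second complete assessment in the same visit window could supply the value (SAP Appendix 2.1). And a blank beside a zero area may mean that the region was not fully examined.

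Most of this stands as a limit on likely size. It does not justify discarding a value that is known.

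Three stronger readings are tempting and should not be drawn.

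- **Bias toward no effect.** A reader might infer that blanks cluster in clear regions, hence in responders, hence in the etrasimod arm. Nothing in the documents supports the first step. An estimate built on it, such as a 30-point difference falling to between 29.3 and 25.2, needs assumed response rates, an assumed share of responders with a clear region and an assumed blank rate.
- **Loss of the baseline.** SAP 3.4 and Table 8 fall back to the last non-missing value before dosing, and EASI is also scored at screening. A blank on Day 1 therefore substitutes an earlier score; the participant is not lost.
- **Replacement by the plain placebo mean under E2.** The imputation conditions on the participant's earlier visits. Gaps followed by observed double-blind data are imputed as missing at random, with no jump to placebo.

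**Conclusion.** The point holds in a limited form. The written rule discards EASI scores that the recorded data determine, and in the Part 1 double-blind and extension phases it then counts certain EASI-75 and EASI-90 responders as failures, at 3.3 points of the arm's rate each with 30 per arm. Under E2 it replaces a determined etrasimod value at Week 16 with an imputation built on placebo means.

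The primary IGA endpoint is scored separately and is not touched. In Part 2, and in the observed-data descriptive tables, the participant leaves the summary and is not counted as a failure.

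The frequency of blanks and their split between arms are unknown, so neither an overall size nor a direction of bias can be given. If the CRF forces zeros to be entered, nothing changes in practice.

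**What to change.** In SAP Appendix 2.2.3, state that a region's subscore is 0 when its Area Score is 0, or when all four of its sign scores are 0, regardless of anything else missing in that region. State that EASI is missing only if a missing component could change its value. Make the change before treatment assignments are released for the interim analysis. Total BSA can stay missing when handprints are missing, as Appendix 2.2.2 has it.

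The cost is two sentences and a few lines of derivation code, with no new data and the same treatment of both arms. The small downside is that a blank beside a zero area may reflect an incomplete examination. Query the blank with the site first, and apply the rule only to blanks that remain. Reporting the number of scores recovered, by arm and visit, would show whether the rule mattered.

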Appendix 2.2.4. Peak Pruritus Numerical Rating Scale (PP-NRS)

PP-NRS is a single-item on the scale from 0 (no itch) to 10 (worst itch imaginable), NRS rating scale, to assess itch at the worst moment during the previous 24 hours. The following binary efficacy endpoint will be derived: ≥4-point reduction from baseline in PP-NRS. Only participants with baseline PP-NRS ≥4 are included in all analyses of this endpoint. If PP-NRS score is missing for a visit, the derived endpoint will also be missing at that visit.

Appendix 2.2.5. Skin Pain Numerical Rating Scale (Skin Pain NRS)

The Skin Pain NRS is a single-item on the scale from 0 (no skin pain) to 10 (worst skin pain imaginable), NRS rating scale, to assess the skin pain at its worst over the previous 24 ours. The following binary efficacy endpoint will be derived: ≥4-point reduction from baseline in Skin Pain NRS. Only participants with baseline Skin Pain NRS ≥4 are included in all analyses of this endpoint. If Skin Pain NRS score is missing for a visit, the derived endpoint will also be missing at that visit.

Appendix 2.2.6. Patient-Oriented Eczema Measure (POEM)

POEM is a 7-item measurement used for monitoring symptom severity of atopic eczema. To address severity, the POEM measures 7 aspects of the experiences of participants with eczema including skin itch, sleep disturbance, skin bleeding, weeping/oozing of the skin, cracked skin, flaking skin, and skin dryness/roughness. Participants are asked to answer based on the number of days they experienced each on a 5-point scale (0=No days, 1=1 to 2 days, 2=3 to 4 days, 3=5 to 6 days, and 4=everyday) over the past week based on recall. The scores from the 7 questions are accumulated to provide an overall POEM score with a range of 0 to 28. An overall POEM score is as follows: 0 to 2 = 'clear/almost clear'; 3 to 7 = 'mild'; 8 to 16 = 'moderate'; 17 to 24 = 'severe'; and 25 to 28 = 'very severe' atopic eczema.

POEM is measured at baseline, Weeks 16, 32, and 68 in Part 1; baseline, Weeks 24 and 52 in Part 2. The following efficacy endpoints will be derived using POEM:

- Change from baseline in POEM.
- \geq 4-point reduction from baseline in POEM. Only participants with baseline POEM \geq 4 are included in all analyses of this endpoint.

If POEM score is missing at a visit, the derived endpoints will also be missing at that visit.

Appendix 2.2.7. Range of Values for Continuous Efficacy Endpoints

The following table displays the unit, theoretical range of values, and the direction of improvement for each of select continuous efficacy endpoints.

Table 13. Numerical Characteristics of Select Continuous Scores and Derived Effiacy Endpoints

Endpoint	Unit	Theoretical Range of Values	Direction of Improvement from Baseline
IGA	None	0-4	Decrease from Baseline
Total BSA	%	0-100	Decrease from Baseline
EASI	None	0-72	Decrease from Baseline
PP-NRS	None	0-10 (NRS)	Decrease from Baseline
Skin Pain NRS	None	0-10 (NRS)	Decrease from Baseline
POEM	None	0-28	Decrease from Baseline

Appendix 3. Efficacy Data Set Descriptions For Part 1 Double-Blind Phase

There are two intercurrent events considered for Part 1 DB phase of this study, (1) the initiation of prohibited medications, and (2) the discontinuation of the study treatment (etrasimod 2 mg QD or placebo) due to any reason.

During the Part 1 DB phase, if a participant initiates prohibited medications (intercurrent event 1 above) and/or discontinues study treatment due to any reason (intercurrent event 2 above), the date of the earlier intercurrent event is noted (as recorded on relevant CRF page) and is used to differentiate and to define the data up to Week 16 into "Pre-intercurrent-event data", "Post-intercurrent-event data" (ie, both Pre- and Post-intercurrent-event data together), as laid out in the table below. Only efficacy data are in scope for this data differentiation.

Table 14. Efficacy Data Set Differentiation by Estimand in Part 1 DB Phase

Estimand	Participants who initiate prohibited medications and/or discontinue study treatment due to any reason prior to Week 16	Participants who do not experience any intercurrent events
E1	For this participant, the date/day of the earlier intercurrent event is flagged and noted (eg, Day X relative to baseline Day 1). Only data collected/assessed on or before Day X+2 (ie, allowing up to 2 additional days after date of earlier intercurrent event), as pre-intercurrent-event data, are included in this dataset. Any data collected/assessed after Day X+2, as post-intercurrent-event data, are excluded in this dataset. Visit windowing is performed after this data differentiation on the Pre-intercurrent-event data.	All data (unaffected due to no intercurrent events) of these participants will be included.
E1a	All data of these participants will be included regardless of the intercurrent events.	Same as E1 above.
E2	Same as E1 above.	Same as E1 above.
E2a	Same as E1a above.	Same as E1a/E1 above.
No Estimand	All data of these participants and available data will be inclu-	ded regardless of the intercurrent events.

All efficacy data collected in Part 1 OLE phase and Part 2 OL Safety phase will include all data collected/assessed regardless of these intercurrent events (ie, no estimand defined). All safety data will be analyzed regardless of these intercurrent events.

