9.1.1. Estimands

9.1.1.1. Primary Estimand

The primary estimand (E1) is defined by the following attributes:

- 1. Treatment condition: received study intervention of etrasimod 2 mg QD or placebo.
- 2. Population: Participants with moderate-to-severe AD as defined by the inclusion and exclusion criteria.
- 3. Variables: Proportion of participants achieving IGA score of clear (0) or almost clear (1) and a reduction from baseline of ≥2 points at Week 16. A participant who experiences an intercurrent event of initiation of prohibited medications or discontinuation of study treatment due to any reason (whichever is earlier), will be considered an IGA non-responder (ie, treatment failure) at Week 16.

4. Intercurrent Events:

- A) Initiation of prohibited medications a participant who receives prohibited medication post-randomization prior to the Week 16 visit will be considered an IGA non-responder (ie, treatment failure) at Week 16.
- B) Discontinuation of study intervention due to any reason prior to the Week 16 visit a participant who discontinues study intervention due to any reason will be considered an IGA non-responder (ie, treatment failure) at Week 16.
- 5. Population level summary: The difference in IGA response rates at Week 16 between etrasimod 2 mg QD and placebo.

Estimand E1 will be similarly applied to the binary secondary endpoint (ie, EASI-75 at Week 16) as well as the binary exploratory endpoints (eg, ≥4-point reduction from baseline in PP-NRS score at Week 16) with the endpoint substituted appropriately.

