2.1. Modifications to the Analysis Plan Described in the Protocol

There are no modifications in this SAP (Version 2, 28 Jul 2023) to the analysis plan described in the protocol amendment 2 (17 May 2023).

The previous SAP version (Version 1, 15 Mar 2023) was written based on the most recent approved protocol (protocol amendment 1, 07 Dec 2022) and other protocol-related documents (eg, PACL) preceding this SAP (Section 1). This SAP was intended to provide more details on statistical methodology and analyses in accordance to the study objectives (Section 2.2). This SAP also further clarified or modified what was outlined in the protocol version where appropriate. These clarification or modification are provided in the table below.

Table 2. Clarification and Modification to Statistical Concepts or Methods Outlined in Protocol Amendment 1, 07 Dec 2022

Section of	Protocol Description	Clarification or Modification
Protocol	-	
Section 1:	The intercurrent events for Estimand E1 and	The intercurrent events for Estimand E1 and
Protocol	E2 are "the benefit of additional prohibited	E2 are updated to "initiation of prohibited
Summary,	medications and regardless of treatment	medications or discontinuation of study
Section 3:	compliance."	treatment" (whichever is earlier) to reflect
Estimands		the intention to objectively account for these
		two post-randomization events for these two
		estimand strategies. These changes are
		detailed in Section 2.2 and Appendix 3.
Section 1:	Under Exploratory Objectives for Part 1	The definitions of baseline for Part 1 and
Protocol	OLE and Part 2, "Baseline, for efficacy	Part 2 are different. The baseline described in
Summary,	endpoints, is defined as pre-dose Day 1 in	protocol is for Part 1 only, since Part 2 is a
Section 3:	the double-blind phase."	separate part of the study with de novo
Estimands		participant enrollment. Baseline for Part 2 is
		the pre-dose Day 1 in the Part 2 OL phase.
		These changes are detailed in Section 2.2 and
		Section 3.4.

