2.2.1. Primary Estimand

There are two intercurrent events considered for Part 1 DB phase of this study, (1) the initiation of prohibited medications, and (2) the discontinuation of the study treatment (etrasimod or placebo) due to any reason. Estimand E1 is an estimand strategy for a binary endpoint at a visit, when applied to the primary endpoint of IGA response at Week 16, it is known as the primary estimand. Estimand E1 is illustrated using the primary endpoint below.

Estimand E1 for a binary endpoint at a visit:

Estimand E1 uses a composite strategy and estimates the treatment effect at a visit considering a participant as non-responder after experiencing the intercurrent event of initiation of prohibited medications or discontinuation of study treatment. The primary estimand is Estimand E1 applied to the primary endpoint of IGA response at Week 16, and is defined according to the primary objective. The primary estimand is defined by the following five attributes:

- 1. Treatment condition: received study intervention of etrasimod 2 mg QD or placebo.
- 2. Population: Participants with moderate-to-severe AD as defined by the inclusion and exclusion criteria.
- 3. Variable: IGA response at Week 16 is score of clear (0) or almost clear (1) and a reduction from baseline of ≥2 points. A participant who experiences the intercurrent event of initiation of prohibited medications or discontinuation of study treatment due to any reason (whichever is earlier), will be considered an IGA non-responder (ie, treatment failure) at Week 16.

4. Intercurrent events:

- Initiation of prohibited medications a participant who receives prohibited medications post-randomization prior to the Week 16 visit will be considered an IGA non-responder (ie, treatment failure) at Week 16.
- Discontinuation of study intervention due to any reason prior to the Week 16 visit

 a participant who discontinues study treatment due to any reason will be
 considered an IGA non-responder (ie, treatment failure) at Week 16.
- 5. Population-level summary: The difference in IGA response rates at Week 16 between etrasimod 2 mg QD and placebo.

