5.3. Methods to Manage Missing Data

In Part 1 DB phase, after accounting for relevant intercurrent events in the data sets (Section 2.2, Appendix 3) and visit windowing (Appendix 2.1) in the data, if a binary efficacy endpoint at a visit has missing value, it will be handled by setting the missing binary efficacy DMB02-GSOP-RF02 7.0 Statistical Analysis Plan Template 31-Jan-2022

endpoint to non-response. This method of handling missing binary efficacy endpoint is known as missing response as non-response (MR=NR). In general, if a continuous efficacy endpoint at a visit has missing value, it will remain missing and no imputation of this missing value will be performed in the datasets.

Under Estimand E1 (eg, IGA response at Week 16), after accounting for the occurrence of relevant intercurrent events in the dataset and in the FAS, missing binary efficacy endpoint at a visit will be set to non-response (ie, treatment failure). If intercurrent events have not occurred before a visit, and the binary efficacy endpoint at this visit has missing value, it will be set to non-response due to MR=NR. Under the Estimand E1a, since intercurrent events are not considered, if the binary efficacy endpoint at a visit has missing value, it will be set to non-response due to MR=NR.

For continuous efficacy endpoint analyzed under Estimand E2 (eg, percent change from baseline in EASI score at a visit), after accounting for the occurrence of relevant intercurrent events, the post-intercurrent-event data will be treated as missing, only pre-intercurrent event data will be included in the JTC method via multiple imputations (Section 5.2.2.1).

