1) Week 16 Completers with Observed Non-Response	xx (xx.xx)	xx (xx.xx)	
2) Week 16 Completers with Missing Response Set as Non-Response	xx (xx.xx)	xx (xx.xx)	
3) Initiation of Prohibited Medications Prior to Week 16 Visit (Earlier)	xx (xx.xx)	xx (xx.xx)	
4) Discontinued Study Treatment Due to Any Reason Prior to Week 16 Visit (Earlier)	xx (xx.xx)	xx (xx.xx)	
Reasons for Discontinuation of Study Treatment [2]			
Lack of Efficacy	xx (xx.xx)	xx (xx.xx)	
Adverse Event	xx (xx.xx)	xx (xx.xx)	
Death	xx (xx.xx)	xx (xx.xx)	
Lost to Follow-up	xx (xx.xx)	xx (xx.xx)	
Withdrawal by Subject	xx (xx.xx)	xx (xx.xx)	
Non-Compliance with Study Drug	xx (xx.xx)	xx (xx.xx)	
Protocol Deviation	xx (xx.xx)	xx (xx.xx)	
Pregnancy	xx (xx.xx)	xx (xx.xx)	
Physician Decision	xx (xx.xx)	xx (xx.xx)	
Medication Error without Associated Adverse	xx (xx.xx)	xx (xx.xx)	
Event			
Study Terminated by Sponsor	xx (xx.xx)	xx (xx.xx)	
Other	xx (xx.xx)	xx (xx.xx)	

^[1] N = number of participants in the FAS with Baseline IGA \geq 2. IGA response rates are calculated based on this as denominator.

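### For the primary responder endpoint the SAP gives two conflicting rules for an intercurrent event shortly before the Week 16 visit and does not say which prevails

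*SAP*

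**What the plan says.** **The estimand.** SAP 2.2.1 states: "Estimand E1 uses a composite strategy and estimates the treatment effect at a visit considering a participant as non-responder after experiencing the intercurrent event". For prohibited medication, "a participant who receives prohibited medications post-randomization prior to the Week 16 visit will be considered an IGA non-responder". Stopping treatment before that visit is handled the same way in Protocol 9.1.1.1: "a participant who discontinues study intervention due to any reason will be considered an IGA non-responder (ie, treatment failure) at Week 16". The shell for Table 4 (SAP 6.1.2) lists, beneath the non-responder heading, a row for prohibited medication and a row reading "4) Discontinued Study Treatment Due to Any Reason Prior to Week 16 Visit (Earlier"). None of these passages allows extra days.

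**The derivation.** Table 14 in SAP Appendix 3 defines the E1 data set for a participant whose earlier event falls on Day X: "Only data collected/assessed on or before Day X+2 (ie, allowing up to 2 additional days after date of earlier intercurrent event"). These records are labelled pre-intercurrent-event data, and windowing is applied to them afterwards. SAP Appendix 2.1 lets unscheduled and early termination assessments fill an analysis visit. The Week 16 window opens on Day 99 and closes on Day 126 if there is no treatment switch. SAP 5.3 then says "missing binary efficacy endpoint at a visit will be set to non-response (ie, treatment failure"). SAP 6.1.1 ties the primary analysis to the Appendix 3 data set.

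**The link between them.** SAP 5.3 handles missing data "after accounting for relevant intercurrent events in the data sets (Section 2.2, Appendix 3) and visit windowing (Appendix 2.1) in the data". It cites the estimand section and the data-set appendix together and ranks neither. SAP 2.1 adds: "There are no modifications in this SAP (Version 2, 28 Jul 2023) to the analysis plan described in the protocol amendment 2".

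**The concern.** Two programmers can each follow the SAP and give the same participant opposite values of the primary endpoint. One applies 2.2.1 directly and sets anyone with an event before the Week 16 visit to non-response. The other makes the Day X+2 cut, windows what remains and converts missing values. The second route can leave a late-event participant as a responder, contrary to the primary estimand and to the categories of Table 4.

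EASI-75 at Week 16 and the exploratory E1 endpoints use the same derivation. The IGA result also feeds the go/no-go decision on Part 2. Timing matters too. The study team is unblinded at the formal interim analysis, earlier unblinded looks are allowed, and the double-blind analysis is repeated on the final database (SAP 5 and 7). A conflict first noticed at quality control, for example when Table 4 fails to reconcile, could be settled with treatment codes known.

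E2 is not affected, because SAP 2.2.2 defines its post-event data by reference to Appendix 3.

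**Working it through.** **1. The plan's own precision figures (Protocol 9.5).** With n = 30 per arm and response rates of 9% and 39%:

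- Per arm: 1.96 × √(0.39 × 0.61/30) = 17.5%; 1.96 × √(0.09 × 0.91/30) = 10.2%.
- Difference: 1.96 × √(0.39 × 0.61/30 + 0.09 × 0.91/30) = 20.2%.

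Both stated figures reproduce. They do not depend on which rule is used.

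**2. Where the rules part.** They differ when an IGA falls in the Week 16 window on or before Day X+2, is a response, and the event precedes the Week 16 visit. The window opens on Day 99, so if the two days are used the earliest such event is Day 97.

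| Case (IGA 0/1 with ≥2-point reduction) | SAP 2.2.1 and Table 4 | Table 14, Appendix 2.1 and 5.3 |
|---|---|---|
| Stops Day 100, early termination visit Day 102 | Non-responder | Kept (X+2), in window, not missing: responder |
| Prohibited medication Day 111 or 112, attends Day 113 | Non-responder | Kept, in window, not missing: responder |

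An unscheduled in-window assessment made before the event also survives the second route, without needing the two days.

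**3. Expected size, discontinuations.** The documents give no event rate, so these are assumptions:

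- 10-30% of each arm (3 to 9 of 30) have an event, uniform over Days 1 to V−1.
- The visit day V is 108 to 118 (Day 113 ± 5, Schedule of Activities).
- All events are discontinuations, with the early termination visit uniform over Days X to X+7 (the Schedule of Activities asks for it within 1 week of last dose).

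Qualifying day-pairs are 1 (X = 97) + 2 (X = 98) + 3 × (V − 99). The share is this count ÷ 8 ÷ (V − 1).

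| V | Day-pairs | Share | × 3 to 9 events |
|---|---|---|---|
| 108 | 30 | 30/8/107 = 3.50% | 0.11 to 0.32 |
| 113 | 45 | 45/8/112 = 5.02% | 0.15 to 0.45 |
| 118 | 60 | 60/8/117 = 6.41% | 0.19 to 0.58 |

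Applying the planned response rates to the full range of 0.105 to 0.577 participants:

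- Placebo: × 0.09 = 0.01 to 0.05 participants; ÷ 30 = 0.03 to 0.17 points.
- Etrasimod: × 0.39 = 0.04 to 0.23 participants; ÷ 30 = 0.14 to 0.75 points.

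**4. Expected size, prohibited medication.** If instead all events are prohibited-medication starts with an attended visit, only the two days before the visit qualify: 2/107 = 1.87% to 2/117 = 1.71%. With 3 to 9 events that is 0.05 to 0.17 participants per arm, before requiring a response.

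**5. One actual case.** 1/30 = 3.3 points, or 3.3/20.2 = 0.165 of the planned half-width. As an illustration using the CMH formula of SAP 5.2.1.1, take 15 participants per arm in each stratum, with responders (7, 5) on etrasimod and (2, 1) on placebo:

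- As counted: 30.0 (95% CI 9.6 to 50.4).
- One etrasimod responder reclassified in the first stratum: 26.7 (6.4 to 46.9).
- One reclassified in the second stratum instead: 26.7 (6.7 to 46.6).

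**The case against.** The best defence is that Table 14 is a record filter and SAP 2.2.1 is the outcome definition, so both can apply: build the data set, then set anyone with an earlier event to non-response. Some text leans this way. SAP 6.1.1 says the primary analysis is based on E1 and accounts for the events. SAP 5.3 describes missing-as-non-response separately for visits with no earlier event, and Table 4 keeps missing responses and events in separate rows. On this reading SAP 2.1 is correct, because nothing has changed. Table 4 is also only a shell, and the SAP is allowed to modify the protocol's outline.

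The reading is possible, but it needs an override step that no sentence states. It would also leave the two-day allowance with no effect on E1 at the affected visit, although Table 14 writes that allowance in the E1 row. Appendix 2.1 points the other way: it treats events as accounted for once the cut is made. The permission to modify does not settle the matter either, since Protocol Section 9 requires major modifications of the primary endpoint definition to appear in a protocol amendment.

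Two parts of the objection stand. The expected effect is small, and applying the planned response rates to people who stop or start prohibited medication has no support in the documents. The allowance may also have a purpose. Participants are told not to dose before the Week 16 visit (Protocol 6.5), so a completer's last blinded dose precedes that visit, and a bare override keyed to last-dose date could misclassify completers. The SAP gives no such reason, but the fix has to protect them.

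**Conclusion.** The concern holds. The stated derivation can give a primary-endpoint value contrary to the primary estimand, and the SAP does not say which governs. This is an error in the text as written, not merely missing detail.

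The expected misclassification is 0.01 to 0.05 participants on placebo and 0.04 to 0.23 on etrasimod if all events are discontinuations. It rests on the assumed event rates, uniform timing and planned response rates set out above. A single real case would shift an arm by 3.3 points. Planned precision is unaffected. It should be fixed because it concerns the primary endpoint and costs little, not because a large bias is expected.

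**What to change.** Add two statements to SAP 5.3 and to the E1 row of Table 14:

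1. For E1 binary endpoints, an intercurrent event dated before the Week 16 visit (or before the relevant earlier visit) gives non-response at that visit and at later double-blind visits, whatever data the Day X+2 cut and windowing retain.
2. Participants who complete double-blind dosing and attend Week 16 are not discontinuers for this rule.

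Leave E2 as it is. It would also help to name the reference date for participants with no Week 16 visit, and the CRF page that supplies the discontinuation date.

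If the sponsor does intend the two-day allowance to count for E1, it should be written into the E1 definition in both SAP 2.2.1 and the protocol, and Table 4 aligned with it.

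The recommended route costs two sentences. It needs no new data and changes neither study conduct nor the protocol estimand. It should be settled before any unblinded analysis.
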